8.2.4 Blood collection

Three blood samples will be collected from eligible participants who have completed the consent form and baseline survey.

Sample 1

The baseline blood sample will be collected in winter to early spring: (Jun - Sept 2022). Eligible participants will be required to provide a baseline blood sample before the end of September in order for randomisation to take place.

Samples 2 and 3

The second and third samples will be collected at end of summer (Feb – March 2023), and at the end of the intervention phase (winter to early spring: Jul – Sept 2023).

Participants will be provided with either online (printable) or paper pathology collection forms to be presented at their local participating pathology laboratory. Blood samples will then be returned to QIMR Berghofer for processing and storage.

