10.1 Sample Size

We have based our sample size calculations on the ANCOVA analyses, considering the following factors:

- 1. A minimum difference in 25(OH)D concentration between treatment groups of 10 nmol/L; this is beyond the margin of assay error and a smaller difference is unlikely to be clinically relevant.
- 2. 90% power and 5% significance using a one-tailed test. A one-tailed test is appropriate because if sunscreen use increases 25(OH)D concentration this will not be of clinical or public health relevance (given the very high 25(OH)D needed before toxicity occurs).
- 3. Correlation between baseline and subsequent 25(OH)D values of 0.6 and standard deviation of 20 nmol/L: Based on a study in which 25(OH)D was measured on 333 participants from Brisbane and Canberra in all 4 seasons ([name], personal communication).
- 4. Non-compliance in the intervention group of 20%, and 10% uptake of daily sunscreen application in the control group.
- 5. Loss to follow-up of 20%.

The sample size required per group is 115. We require fully powered analyses within tertiles of ambient UVR and baseline 25(OH)D in order to devise appropriate public health and clinical messages. Thus the total sample size to be recruited is 345 per group (690 in total). With 552 participants (80%) completing the study the non-inferiority margin (90% power, α =0.05) is 4.5 nmol/L.

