10.3 Statistical Analysis Plan

Intention-to-treat analyses: Our main analyses will follow an intention-to-treat approach. 25(OH)D values in the Australian population are approximately normally distributed so we will model 25(OH)D as a continuous outcome using longitudinal analysis of covariance (ANCOVA). We will include treatment group (daily sunscreen or control), time, and the

interaction between treatment and time to estimate the difference in 25(OH)D concentration between treatment groups at the end of summer and at the end of winter. This method has been shown to reliably estimate the effect of treatment, accounting for any differences in the baseline value of the outcome measure.³³ All models will be adjusted for the variables used to stratify the randomisation and will include baseline 25(OH)D concentration as a covariate and participant as a random effect.

We will perform the analyses within the whole cohort and separately within tertiles defined according to: (1) average ambient UVR; and (2) baseline 25(OH)D concentration.

The incidence of skin lesions between the two groups will be assessed using Poisson regression.

Sensitivity analyses: To assess the effect of lack of compliance with the sunscreen intervention in the sunscreen group, and any routine sunscreen use in the control group, we will perform:

(a) An as-treated analysis using propensity score adjustment to minimise confounding. We will categorise sunscreen use into low (<30% of eligible days), moderate (30 to <70%), and high (\geq 70%). A generalised boosted model will be used to estimate the propensity score for sunscreen use, from which we will derive inverse probability of treatment weights. These will be used as weights in the ANCOVA models, both overall and within strata.

(b) Instrumental variable principal stratification to estimate the complier average causal effect, using the randomised allocation as the instrumental variable.³⁴ This method preserves the randomisation

Those in the intervention group will be classified as compliant if they used sunscreen on at least 70% of eligible days, and those in the control group will be classified as compliant if they used sunscreen on fewer than 20% of eligible days.

11 Responsibilities

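### The Section 10.3 model, fitted in the standard way, gives the summer and winter contrasts one pooled standard error, which miscalibrates both intervals if residual variance differs by season

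*Protocol*

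**What the plan says.** Protocol Section 10.3 describes a longitudinal ANCOVA. Its fixed effects are introduced with "We will include treatment group (daily sunscreen or control), time, and the" treatment-by-time interaction, and the aim is to estimate the difference "between treatment groups at the end of summer and at the end of winter". All models also adjust for the stratification variables and "include baseline 25(OH)D concentration as a covariate and participant as a random effect". The same analysis is repeated within tertiles. No baseline-by-time term is listed. Nothing is said about whether residual variance may differ between visits or how standard errors are obtained.

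On timing, Section 8.2.4 states: "The baseline blood sample will be collected in winter to early spring: (Jun - Sept 2022". Sample 2 falls in February to March 2023 and sample 3 in July to September 2023. Section 7.6 says that a person's level changes little between years but moves with the seasons.

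For planning, Section 10.1 gives a single set of values for both follow-up visits: "Correlation between baseline and subsequent 25(OH)D values of 0.6 and standard deviation of 20 nmol/L".

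**The concern.** Sample 3 repeats the baseline season one year later, while sample 2 comes from the opposite season. On the reasoning of Section 7.6, baseline should predict the winter value better than the summer value. If total variances are similar, more variance is then left unexplained in summer. A random-intercept fit with one residual variance cannot show this and reports the same standard error for both contrasts.

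The primary aim can be met at either season, so each seasonal contrast can carry the trial's claim by itself. An interval that is too narrow in the noisier season overstates the evidence there, whether that evidence is read as harm or as reassurance. An interval that is too wide in the other season wastes information, and the tertile analyses, which are meant to be fully powered, use the same model.

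**Working it through.** **Inputs from Section 10.1.** Difference 10 nmol/L ("A minimum difference in 25(OH)D concentration between treatment groups of 10 nmol/L"); "90% power and 5% significance using a one-tailed test"; SD 20 and correlation 0.6; "Non-compliance in the intervention group of 20%, and 10% uptake of daily sunscreen application in the control group"; 20% loss to follow-up.

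**The plan's own figure.** Diluted difference = 10 × (1 − 0.2 − 0.1) = 7. Residual SD = 20 × √(1 − 0.6²) = 16. n per arm = 2 × (1.645 + 1.282)² × 16² / 7² = 89.5, so 90. Allowing for dropout, 90 / 0.8 = 112.5, so 113; a t-based calculation gives 91 / 0.8, so 114. The stated 115 is reproduced to within two. Completers per arm are 115 × 0.8 = 92 in a tertile and 552 / 2 = 276 overall.

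**What the pooled model reports.** With complete data and two visits, the random-intercept fit works on the mean and the difference of the two follow-up values. For residuals e1 and e2, the variance attached to each seasonal contrast is proportional to Var((e1 + e2)/2) + Var(e1 − e2)/4 = (σ1² + σ2²)/2. Both contrasts therefore get the average of the two seasonal residual variances.

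**Assumed seasonal values.** The protocol has none. Take SD 20 at every visit and baseline correlations of 0.5 with summer and 0.7 with winter, which average to the stated 0.6. The common slope is 0.6, and the residual variance at visit t is 400 × (1 + 0.36 − 1.2 × r_t).

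- Summer: 400 × (1.36 − 0.60) = 304.
- Winter: 400 × (1.36 − 0.84) = 208.
- Pooled: (304 + 208)/2 = 256.

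Reported over true standard error is √(256/304) = 0.918 in summer (8% too small) and √(256/208) = 1.109 in winter (11% too large). Actual one-sided error is 1 − Φ(1.645 × ratio), which gives 6.6% in summer and 3.4% in winter.

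**Range of assumptions** (SD 20 unless stated):

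| Assumption | Summer error | Winter error |
|---|---|---|
| r = 0.55 / 0.65 | 5.8% | 4.2% |
| r = 0.5 / 0.7 | 6.6% | 3.4% |
| r = 0.45 / 0.75 | 7.3% | 2.6% |
| SD 22 / 18, r = 0.6 | 6.6% | 3.3% |

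Simulation of 10,000 trials with 276 per arm gave 6.8% and 3.4% for r = 0.5/0.7. Fitting each season with its own slope and variance gave 5.2% and 5.1%.

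**Tertile power at r = 0.5/0.7, 92 per arm, difference 7.** The pooled standard error is √(2 × 256/92) = 2.359, so the rejection threshold is 1.645 × 2.359 = 3.881.

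- Winter, pooled: Φ((7 − 3.881)/√(2 × 208/92)) = 92.9%. With its own slope the variance is 400 × (1 − 0.49) = 204, and power is Φ(7/√(2 × 204/92) − 1.645) = 95.3%.
- Summer, pooled: Φ((7 − 3.881)/√(2 × 304/92)) = 88.8%. With its own slope the variance is 400 × (1 − 0.25) = 300, and power is 86.3%. The higher pooled figure comes from a standard error that is too small. That both summer figures fall below 90% follows from the assumed correlation of 0.5, not from the choice of model.

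**Slope difference alone.** With residual SD 16 in both seasons and slopes 0.4 and 0.8, simulation (276 per arm) gave a model standard error of 1.405 against empirical values of 1.410 and 1.429, with one-sided error 5.2% and 5.4%. The season-specific standard error is 1.363, and 1.405/1.363 = 1.03: about 3% of precision is lost and calibration holds.

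**False claim in at least one season.** Using variances 304/208 and an assumed correlation of 0.4 between the two seasonal estimates, the probability is 9.10% with the pooled standard error and 9.05% with correct ones. For correlations of 0.2 to 0.6 the increase is 0.01 to 0.11 percentage points. At r = 0.45/0.75 it is at most about 0.25 points.

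**The case against.** The strongest reply is that the protocol fixes less than this suggests. A participant random effect is compatible with time-specific residual variances or robust standard errors, and such detail commonly sits in a statistical analysis plan, which is not available here. This stands in part: the single residual variance is the default reading, not a stated choice. The single baseline term, however, is on the page.

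Second, no figure in the protocol shows unequal residual variance. Section 10.1 gives one SD and one correlation, although its source study measured all four seasons. This also stands. Sections 7.6 and 8.2.4 give a qualitative reason to expect a difference, and its size is assumed.

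Third, the consequences are limited. The two seasonal errors move in opposite directions and nearly cancel for the either-season claim, and winter tertile power stays above 90%. For the endpoint averaged over both time points (Section 4.3), the pooled standard error is correct with complete data. All of this stands.

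A reader might go further and infer that the standard errors are wrong whenever summer and winter differ in any way. The protocol does not support that. The time term absorbs a difference in means, and a difference in baseline slope alone leaves the standard errors essentially right. Only unequal residual variance given baseline miscalibrates them.

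**Conclusion.** The point holds as a limited, conditional weakness of the stated model. Under the standard fit, both seasonal contrasts share one standard error. For the assumed correlations and SDs examined, one-sided error is about 5.8% to 7.3% in the more variable season and 2.6% to 4.2% in the other. The miscalibration matters when one season's interval or p-value is read by itself, as the primary aim and the tertile analyses invite.

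The effect estimates are unbiased under randomisation, whole-cohort power stays well above 90%, and the overall chance of a false either-season claim is almost unchanged. These results assume complete data, model-based standard errors and the seasonal values stated. If residual variances are equal, or the analysis plan already allows them to differ by visit, the calibration problem disappears. The change is worth making because it is nearly free, not because an error has been shown to occur.

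**What to change.** In Section 10.3, replace the participant random intercept with an unstructured 2x2 residual covariance for the two follow-up visits, and add a baseline-by-time interaction. Time-specific residual variances or robust standard errors are acceptable alternatives for the covariance part. Keep the other terms, and use the same model in the whole cohort and in every tertile. If an analysis plan already says this, align the protocol text with it.

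The cost is two extra parameters with about 552 completers and a small change of code. Section 7.2 has the code finalised on data with scrambled allocation before the real run, so the structure should be settled by then. The corrected summer interval may be wider than the pooled one; that reflects the true uncertainty and is not a loss caused by the change.

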4.3 Study endpoint measures

- 25(OH)D concentration at end of summer and end of winter, and averaged across these time points.
- Compliance with sunscreen use.
- Malignant and pre-malignant skin lesions.

5 Study Design

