5.1 Overall Study Design

Phase: Phase 4 RCT to determine effect of sunscreen application on serum 25(OH)D concentration.

Randomisation: Randomised computer-generated randomisation in a 1:1 ratio, stratified using permuted blocks by state of residence (QLD; NSW/ACT; VIC; TAS), age (18-44; 45-70), and sex. We will use cluster randomisation to ensure participants from the same household are randomised to the same study arm.

Control: Standard Cancer Council information to protect the skin when outdoors for more than a few minutes when the UV Index is \geq 3, provided at baseline.

Blinding: Open label. Blood samples and data will be analysed blinded to study group.

Rationale: An RCT is needed to determine the effect of regular sunscreen application, as observational studies are frequently confounded by indication. It would be unethical to use a placebo sunscreen. We will recruit people who are not already using sunscreen routinely to avoid contamination in the control group, and advise that we want them to continue their usual behaviour during the course of the trial.

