8.2.5 Data linkage

Linkage to Medicare Australia will enable capture of information about skin cancer treatments. This data will be used to assess if regular high SPF sunscreen application reduces the incidence of malignant and pre-malignant skin lesions. Data linkage will be sought for the period between enrolment and up to four years post intervention.

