10.2 Analysis Objectives and Endpoints

The **primary aim** is to determine whether participants randomised to provision of a broadspectrum SPF 50+ sunscreen, and advice to apply it to all body parts uncovered by clothing on all days when the UVI is forecast to reach 3, have a lower mean 25(OH)D concentration at the end of either summer or winter than those randomised to usual discretionary sunscreen use.

Secondary aims are to:

- a. Determine whether the intervention affects 25(OH)D concentration at the end of winter or summer within tertiles of:
 - i. Erythemally weighted ambient UV radiation at the postcode of usual residence
 - ii. Baseline 25(OH)D concentration
- b. Identify environmental and participant factors that influence the change in 25(OH)D concentration in sunscreen users.
- c. Assess the effect of frequent sunscreen application on malignant and pre-malignant skin lesions during the study and over the following 2 years.

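### Section 10.3 names Poisson regression for skin-lesion incidence with no allowance for extra-Poisson variation or household co-randomisation, so default standard errors could be wrong in either direction

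*Protocol*

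**What the plan says.** Protocol section 10.3 specifies the lesion analysis in full as: "The incidence of skin lesions between the two groups will be assessed using Poisson regression". No dispersion term, robust variance, offset or household term is attached to it.

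The aim in section 10.2 is: "Assess the effect of frequent sunscreen application on malignant and pre-malignant skin lesions during the study and over the following 2 years". Section 4.3 lists the endpoint only as "Malignant and pre-malignant skin lesions". The data come from claims; section 8.2.5 says: "Linkage to Medicare Australia will enable capture of information about skin cancer treatments". None of these places says whether the unit is a lesion, a treatment, or a person's first event.

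On the design, section 5.1 says: "We will use cluster randomisation to ensure participants from the same household are randomised to the same study arm". The amendment history records, for version 5, that the limit of one person per household was removed, so shared households are to be expected.

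The paragraph before the lesion sentence in section 10.3 says that the models are adjusted for the stratification variables and "will include baseline 25(OH)D concentration as a covariate and participant as a random effect".

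**The concern.** A Poisson model with its default standard errors takes the variance of a person's count to equal its mean. That fits badly if the outcome is a count of lesions or treatments. Eligibility (section 6.3) spans ages 18 to 70, Fitzpatrick types 1 to 4 and four states, and section 2.2 says the states were chosen to make ambient UV vary as much as possible. When individual rates differ, the variance of the counts exceeds the mean. Placing household members in the same arm adds correlation that no model in section 10.3 accounts for.

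The analysis that would be affected is hypothesis 4 (section 2.2), that the intervention lowers lesion incidence. Standard errors that are too small would make a chance difference look like evidence of prevention.

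**Working it through.** **The plan's own figure.** The protocol states no lesion rate, dispersion or sample size for lesions. Its one sample-size figure, 115 per group (section 10.1), concerns 25(OH)D. It can be approximately reproduced: difference 10 × (1 − 0.2 − 0.1) = 7 nmol/L; SD 20 × √(1 − 0.6²) = 16; one-sided 5%, 90% power; n = 2 × 16² × (1.645 + 1.282)² / 7² ≈ 90; 90 / 0.8 ≈ 113. It has no bearing on the lesion analysis.

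**Inputs.** From the protocol: 345 per group (section 10.1) and 1:1 allocation (section 5.1). Assumed: the lesion mean, the dispersion, a two-sided 5% test and the same follow-up for everyone. The one-tailed test in section 10.1 is argued for 25(OH)D only.

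**Reading 1: a count per person.** Let φ be the ratio of variance to mean. The true standard error is √φ times the model-based one, so the true error of a nominal two-sided 5% test is 2 × [1 − Φ(1.96/√φ)].

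| φ (assumed) | √φ | Interval width relative to correct | True error | Coverage |
|---|---|---|---|---|
| 1 | 1.00 | 1.00 | 5% | 95% |
| 1.5 | 1.22 | 0.82 | 11% | 89% |
| 2 | 1.41 | 0.71 | 17% | 83% |
| 3 | 1.73 | 0.58 | 26% | 74% |

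**Check by simulation.** Negative binomial counts with mean m and shape k, so that φ = 1 + m/k; 345 per arm, no treatment effect, 4,000 trials per row, coverage of nominal 95% intervals:

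| m | k | φ | Model-based | Robust |
|---|---|---|---|---|
| 0.05 | 2 | 1.02 | 95.0% | 95.2% |
| 0.05 | 0.5 | 1.10 | 94.2% | 95.4% |
| 0.05 | 0.2 | 1.25 | 92.4% | 94.8% |
| 0.2 | 0.5 | 1.4 | 90.7% | 95.0% |
| 0.2 | 0.2 | 2.0 | 84.0% | 94.8% |
| 1.0 | 2 | 1.5 | 88.8% | 95.2% |
| 1.0 | 0.5 | 3.0 | 73.7% | 94.6% |

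The simulation agrees with the formula. With rare lesions (m = 0.05) little is lost even when risk is very uneven. The robust variance, here at person level, holds its level throughout.

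**Reading 2: any lesion, yes or no, per person.** With risk p, the true standard error of the log risk is √(1 − p) times the Poisson one, so the default interval is too wide. Coverage is 2Φ(1.96/√(1 − p)) − 1.

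| p (assumed) | √(1 − p) | Coverage |
|---|---|---|
| 5% | 0.975 | 95.6% |
| 10% | 0.949 | 96.1% |
| 20% | 0.894 | 97.2% |
| 30% | 0.837 | 98.1% |

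A first-event analysis in which person-time stops at the first lesion is a different case and was not calculated.

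**Households.** The protocol gives neither the share of participants in shared households nor the correlation of lesions within them, so this part cannot be sized. It is not in the figures above.

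**The case against.** The strongest reply is that the protocol names a model family and nothing more. A robust variance, a dispersion scale or a random effect is compatible with the sentence, and the variance estimator for a secondary outcome is commonly left to a separate statistical analysis plan. That stands in part. A reader might infer that the trial is committed to default standard errors and that its intervals are bound to be too narrow. The text supports neither step: it does not state the variance method, it does not define the outcome as a count, and under a yes/no outcome the error runs the other way.

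A second reply is that the participant random effect in section 10.3 already deals with repeated lesions. That statement sits in the 25(OH)D paragraph, beside baseline 25(OH)D as a covariate, and most naturally describes the ANCOVA. Even if it reached the Poisson model, it would not cover households.

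A third reply is that lesions may be rare and the outcome is only secondary. Both points limit the impact. The lesion aim does not drive the sample size, and section 2.1 already cites randomised evidence that sunscreen reduces skin cancers and actinic keratoses. A false-positive lesion result would therefore not change the trial's main conclusion on vitamin D.

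A reader might also see a contradiction between the analysis period in section 10.2, "during the study and over the following 2 years", and section 8.2.5, "Data linkage will be sought for the period between enrolment and up to four years post intervention". There is none. Hypothesis 4 and section 10.2 agree on the analysis horizon, and section 8.2.5 sets an upper limit on the data to be requested.

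**Conclusion.** The point holds conditionally. Section 10.3 fixes a method and leaves out two features that bear on its standard errors: variation beyond Poisson, and the household co-randomisation that the trial itself introduces. If lesions or treatments are counted per person and default standard errors are used, the true error of a nominal 5% two-sided test is about 11% to 26% for assumed variance-to-mean ratios of 1.5 to 3, and close to nominal if lesions are rare. If the outcome is any lesion, yes or no, intervals are somewhat too wide. No single figure can be given, because the protocol contains no lesion rate, dispersion or household data. What makes this more than a missing detail is that one inexpensive addition, a robust variance clustered on household, corrects the standard errors under both readings. It is worth changing, but it concerns a secondary outcome.

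**What to change.** Replace the lesion sentence in section 10.3 with Poisson regression using robust standard errors clustered on household, log person-time as offset, and adjustment for the stratification factors (state, age group, sex). If lesions are counted, negative binomial regression with household-clustered robust errors is an acceptable alternative.

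In the same place, state whether the outcome is a count (of lesions or of treatments) or a first event per person. If it is a first event, end person-time at that event.

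The cost is wording only, with no extra participants or data collection. The downside is that intervals for this secondary outcome may be wider.
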